## Statistical Power and Statistical Analysis

**Statistical power:** For Aim 1, primary endpoint, with an n=75 and 50 completers, we will have >80% chance of detecting a difference in the rate of BMD AP lumbar spine increase of 0.024g/cm^2/y at a 2-sided  $p=0.05$  level. This compares favorably with the rate of BMD AP spine increase of 0.036 g/cm^2/y in a study by Baum *et al.* administering GH for 18 months to hypopituitary subjects with GH deficiency. This was calculated with software developed by co-investigator [REDACTED] for sample size for random slopes models, available in Matlab [REDACTED]. The variance covariance matrix of the random effects,  $\Psi$ , and residual variance,  $\sigma^2$ , were estimated from longitudinal data from Baum *et al.* that had originally been analyzed by [REDACTED]. The variance of the intercept was 0.024, slope 0.000211, covariance 0.00199 and residual variance,  $\sigma^2$ , 0.00092 and an exponential drop-out rate of 0.36/yr, which is greater than we expect. The program uses the fact that the variance covariance matrix for the fixed effects of the model are:  $\mathbf{V(B)} = \{\mathbf{X}'[\sigma^2] + \mathbf{Z\Psi Z}'\}^{-1}\mathbf{X}$ . One incorporates drop outs by replacing  $\mathbf{X}'[\sigma^2] + \mathbf{Z\Psi Z}'\}^{-1}\mathbf{X}$  by a weighted sum for different follow-up times with weights equal to the follow-up probability -- a special case of the general model described in Pinheiro and Bates. For Aim 2, primary endpoint, with 50 completers we can detect 0.81 x SD of the difference in bone marrow fat content over a year; For secondary endpoints: for trabecular thickness (TbTh) and cortical thickness (CoTh), based on our preliminary data in obese men receiving placebo for 6 months in which the standard deviation (SD) of the change in TbTh was 0.0047mm and of CoTh was 0.0015mm, we will be able to detect an annual increase of 0.008mm and 0.012mm, respectively; for FEA we will have a power of 80% at a two-sided  $p=0.05$  significance level, if the true rate of difference in estimated failure load between the treatments is 316 units, based on an assumption that the SD is 570 units, as derived from Boutroy *et al.* With 50 completers, we will have an 80% power at a 2-sided  $p=0.05$  level to see a difference in PINP of 38.6 ng/ml, total abdominal fat of 50.8 cm^2, lean mass of 1.2 kg, vitamin D of 0.025 ng/ml, hsCRP of 0.025 mg/l, and apoB of 18.6 mg/dl per year. These were calculated from our preliminary data administering GH to obese subjects for 6 months. The power for the mediation analyses (see below) depends on the effect size of the treatment on BMD and on the correlation of the secondary endpoint on BMD. We derived a formula using the delta method. With at least 40 subjects we will have an 80% chance of achieving significance at a two-sided  $p=0.05$  level if the effect size is 2 units and the correlation is 0.5. For the 6-month withdrawal period, we will have adequate power to test whether the BMD remains significantly different from placebo at 24 months. We will have 80% power to detect a difference of 0.04 g/cm^2 assuming that there are at least 43 patients still in the study at 18 months (we expect 50).

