
**Data analysis plan:** We will pool data from men and women using a random slopes model; we will consider a model where each patient has a random slope and intercept. The mean intercept and slope may be different for men and women and in each treatment group. The primary analysis is a pooled analysis of treatment effect across gender with weights equaling the frequency of men and women in the sample. A secondary analysis will test for the significance of the treatment-gender interaction on the rate of change of BMD and all other endpoints. For all analyses, an intent-to-treat analysis will be performed. We plan to apply the guidelines developed by the National Research Council regarding missing data. Our primary analysis, the random slopes model, assumes that data is missing at random. We also will conduct two sensitivity analyses. The first assumes that the missing data is a function of the unobserved random effect and the second tests the assumptions in this model under other missingness mechanisms. We will also determine which of the secondary endpoints appears to mediate the treatment effect on an endpoint, such as BMD, microarchitectural parameters, and bone marrow fat by examining the effect of treatment on the potential mediator and of the potential mediator on the endpoint; examples of this will include whether Pref-1 mediates the effects of GH on bone marrow fat or strength, and whether bone marrow fat, body composition variables, inflammatory markers, lipids or vitamin D mediate the effects of GH on bone strength. The effect on one endpoint by a potential mediator is the product of the two effects. The Sobel test will test whether this effect is zero. As there are no known moderators of GH treatment in this population and the population has been purposely selected for osteopenia, we will not control for covariates other than gender in our primary analysis. We will perform exploratory analyses to answer the following: 1. Among an osteopenic population are there covariates

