(such as family history, smoking, alcohol, exercise, free testosterone or estradiol) that predict problems such as anomalies in bone microarchitecture and predicted strength? 2. Are these factors moderators of the treatment effect of GH? Both of these analyses will use stepwise variable selection using a random effects model as above. 3. Is the effect of GH on BMD mediated by IGF1? We will perform a mediation analysis using a random effects model with final GH dose and a final GH dose time interaction in the treated group.

**Timeline:** Screening, enrollment, and study visits will occur from year 1 through year 5. Data management will occur in years 1-5, and analyses and manuscript preparation will be performed in years 4-5.

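### Moderators of the GH effect are to be chosen by stepwise search over an open list, with no entry threshold and no allowance for selection, so the false-finding rate is uncontrolled and selected effects will be overstated

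*SAP*

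**What the plan says.** The SAP's data analysis plan introduces three further questions with "We will perform exploratory analyses to answer the following". The first asks which covariates predict abnormal microarchitecture and predicted strength. The second asks of the same covariates: "Are these factors moderators of the treatment effect of GH". The covariates are given by example only: "such as family history, smoking, alcohol, exercise, free testosterone or estradiol". The method for the two questions is one sentence: "Both of these analyses will use stepwise variable selection using a random effects model as above".

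The statistical section gives no entry or removal threshold, no closed candidate list, no statement of which endpoints will be searched for moderators, and no multiplicity control, shrinkage or resampling for this step. Just before these questions, it explains why the primary analysis adjusts for gender alone: "As there are no known moderators of GH treatment in this population".

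**The concern.** Two separate things go wrong when moderators are picked this way.

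The first is multiplicity. Each candidate has its own chance of crossing the entry threshold when it modifies nothing, and these chances accumulate over the list. Because the SAP states no threshold and does not close the list, nobody can say in advance what the false-finding rate is.

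The second is selection. A term enters the final model only if its estimate happens to be large relative to its standard error. The p-value, interval and coefficient printed for that term take no account of this. With 50 to 75 patients an interaction is estimated imprecisely, so a modest true interaction can be selected only when chance has enlarged it.

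At stake is the answer to the moderator question. A later trial might restrict enrolment or set its sample size on a factor that has no effect, or on an effect stated at two or three times its real size.

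**Working it through.** **Inputs**
- Candidates: six named, list open (SAP, data analysis plan).
- Entry threshold: not stated. I take 0.01 to 0.157 (the AIC equivalent) as an assumed range. Two-sided 0.05 is the only level in the statistical section, and it appears there for power.
- Sample size: "with an n=75 and 50 completers" (SAP, statistical power). Equal arms are assumed.
- Slope variance 0.000211, residual variance 0.00092, treatment effect 0.024 g/cm²/y (SAP, statistical power).
- DXA times 0, 1 and 1.5 years (Protocol, follow-up visits). The 24-month scan falls after the withdrawal period and is left out.

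**Step 1: the plan's own figure.** The SAP states no error rate for the search. The nearest stated figure is for Aim 2: "with 50 completers we can detect 0.81 x SD of the difference in bone marrow fat content over a year". With 25 per arm, two-sided 0.05 and 80% power, the normal formula gives (1.960 + 0.842) × √(2/25) = 0.792 SD. The noncentral t gives 0.809 SD, with 80.1% power at 0.81 SD. The figure reproduces with two arms of 25.

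**Step 2: chance of at least one false moderator.** For one endpoint, no true moderator and k independent candidates, the chance is 1 − (1 − a)^k.

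| Entry p (a) | k = 5 | k = 6 | k = 7 |
|---|---|---|---|
| 0.01 | 4.9% | 5.9% | 6.8% |
| 0.05 | 22.6% | 26.5% | 30.2% |
| 0.10 | 41.0% | 46.9% | 52.2% |
| 0.15 | 55.6% | 62.3% | 67.9% |
| 0.157 (AIC) | 57.4% | 64.1% | 69.7% |

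For example, 1 − 0.95^6 = 0.265. Five candidates applies if smoking is not recorded; seven applies if one more is added under the open list.

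**Step 3: check by simulation.** Forward selection with backward removal was run on treatment-by-covariate terms in patient-level BMD slopes, with sex and main effects forced in and 1,500 trials per setting. Over N = 50 and 75, and independent and correlated covariates, at least one false moderator was selected in 24–28% of trials at entry 0.05, 44–49% at 0.10, 61–63% at 0.15 and 63% under AIC (the AIC setting with correlated covariates was run at N = 50 only). These match the formula and barely change with N. Six separate unadjusted tests would give the same rate. Across all thresholds, 24–31% of these null trials ended with a selected term at nominal p<0.05.

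**Step 4: size of the selected effects.** The sum of squares of the visit times 0, 1 and 1.5 about their mean is 1.1667. The SD of a patient's fitted slope is √(0.000211 + 0.00092/1.1667) = 0.0316 g/cm²/y. The interaction per SD of a covariate is a difference between two arms, so its standard error is about 2 × 0.0316/√N: 0.0089 at N = 50 and 0.0073 at N = 75.

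To enter at p<0.05 with N = 50, an estimate must exceed about 1.96 × 0.0089 = 0.0175. That is 1.46 times a true interaction of 0.012 and 2.92 times one of 0.006. These assumed values are half and a quarter of the 0.024 treatment effect. Simulation with one true moderator (correlated covariates, 700 trials per setting) gave:

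| N | True interaction | Entry p | Selected | Mean selected estimate ÷ truth | Coverage of nominal 95% CI |
|---|---|---|---|---|---|
| 50 | 0.006 | 0.05 | 10% | 3.3 | 63% |
| 50 | 0.006 | 0.15 | 23% | 2.6 | 74% |
| 50 | 0.012 | 0.05 | 23% | 2.1 | 83% |
| 50 | 0.012 | 0.15 | 35% | 1.8 | 85% |
| 75 | 0.006 | 0.05 | 11% | 2.9 | 74% |
| 75 | 0.006 | 0.15 | 30% | 2.6 | 80% |
| 75 | 0.012 | 0.05 | 35% | 1.7 | 89% |
| 75 | 0.012 | 0.15 | 56% | 1.5 | 94% |

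Sample size matters here: overstatement is smaller and coverage better at N = 75. Both simulations used complete data, with patient-level slopes standing in for the full mixed model.

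**The case against.** The strongest defence is that the SAP labels this work exploratory, claims no known moderators, and rests no primary, secondary or sensitivity result on it. That stands, and it limits the importance of the point. It does not make a p-value, interval or estimate obtained after selection correct.

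A reader might infer more than the documents support:
- *That a quarter to two thirds of such trials will name a false moderator.* The SAP gives no threshold. The one level it uses gives about 26%, and 0.01 gives about 6%. With six candidates even 0.15 or AIC stops at 62–64%. All these figures assume one endpoint and no true moderator; searching more endpoints would raise them.
- *That stepwise search or the small sample causes that rate.* Steps 2 and 3 show that it is plain multiplicity. Dropping stepwise selection without adjusting would leave it unchanged.
- *That selected factors will be announced as established moderators.* The SAP does not say how results will be presented.
- *That the same percentages apply to the predictor question.* The simulations covered treatment interactions only. The objection to stepwise selection there rests on the general argument, with no figure.

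It can also be said that strict adjustment is costly in a screen with little power. At N = 50 a true interaction of 0.012 lies 0.012/0.0089 = 1.34 standard errors from zero. Power is about 27% at 0.05 (normal approximation: upper tail beyond 1.96 − 1.34) and about 10% at 0.05/6 (beyond 2.64 − 1.34). That is a fair reason to make adjustment conditional on a claim and not compulsory.

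**Conclusion.** The point holds as a low-severity improvement. As written, the moderator search has no defined error rate. With six candidates, one endpoint and no true moderator, the chance of a false moderator is about 6% at entry 0.01, 26% at 0.05 and 62–64% at 0.15 or AIC. That part is uncorrected multiplicity and does not depend on sample size.

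Separately, selection overstates whatever it keeps: about 1.5–2.1 times for an assumed true interaction of 0.012 g/cm²/y per SD, and 2.6–3.3 times for 0.006. Nominal 95% intervals cover 63–94%. This part does worsen with a small sample, and it depends on the assumed interaction sizes, which are not in the documents. The primary BMD analysis is not affected.

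**What to change.** - Close the candidate list to factors actually collected at baseline. Smoking is named in the SAP but is missing from the Protocol's baseline list of factors affecting BMD. Confirm that it is recorded, for instance in the medical history, or remove it.
- For the moderator question, replace stepwise selection with one prespecified random-effects model per factor, containing the treatment × time × covariate term. The SAP already plans a stand-alone interaction test for gender, so the form is familiar.
- Report every interaction estimate with its 95% CI, labelled hypothesis-generating, and state how many factors and endpoints were examined.
- If any factor is to be called a moderator on a p-value, use a multiplicity-adjusted one such as Holm. For scale, testing six factors at 0.05/6 gives 1 − (1 − 0.05/6)^6 = 4.9% under the assumptions of Step 2.
- For the predictor question, fit one full model with all listed covariates.

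The cost is a few SAP sentences and a few more models, with no new patients or visits and no change to the primary analysis. The downside is fewer nominally significant moderators.

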Skeletal Physiology Dysregulation in Obesity: The Role of Growth Hormone

NCT# 01724489

Version Date: November 7th, 2019

PARTNERS HUMAN RESEARCH COMMITTEE PROTOCOL SUMMARY

Answer all questions accurately and completely in order to provide the PHRC with the relevant information to assess the risk-benefit ratio for the study. Do not leave sections blank.

PRINCIPAL/OVERALL INVESTIGATOR [name]

PROTOCOL TITLE

Skeletal Physiology Dysregulation in Obesity: The Role of Growth Hormone

FUNDING

VERSION DATE 10.16.19

SPECIFIC AIMS

Concisely state the objectives of the study and the hypothesis being tested.

Specific Aim 1: Low-dose GH administration for 18 months to osteopenic obese men and women will increase bone mass, improve bone microarchitecture and increase bone strength.

We will investigate in osteopenic men and women with obesity and relative IGF-1 deficiency, whether GH administration for 18 months to increase IGF-1 levels within the normal range results in:

- A. Increased BMD
- B. Improved bone microarchitecture, including trabecular and cortical thickness.
 - The increase in trabecular thickness will be mediated primarily by GH and the effect on cortical thickness by IGF-1
- C. An increase in bone strength, as determined by finite element analysis

Specific Aim 2: We will investigate mechanisms responsible for the increase in bone strength due to GH administration. We hypothesize that the increase in strength will be mediated by:

- **A.** A reduction in bone marrow fat mediated by a decrease in Pref-1 associated with an increase in osteoblast activity, assessed by markers of bone formation, including P1NP
- B. Increased insulin, in associations with an increase in undercarboxylated osteocalcin
- **C.** Improved body composition, including a decrease in abdominal adiposity and lipid deposits in muscle and liver, and an increase in muscle mass
- D. A reduction in inflammatory cytokines and improvement in the serum lipoprotein apoB
- E. An increase in circulating vitamin D.

BACKGROUND AND SIGNIFICANCE

Provide a brief paragraph summarizing prior experience important for understanding the proposed study and procedures.

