- Blood drawn to determine levels of hormones and other chemicals (3 week, 9 week, 4 month, 6 month, 9 month 12 month, 15 month, 18 month and 24 month visits).
- OGTT (6 month, 12 month, and 18 month and 24 month visits)
- Paffenbarger Physical Activity Questionnaire and Calcium & Vitamin D Frequency Questionnaire (6-month, 12-month, 18-month, 24-month visits)
- Functional Strength Test (6-month, 12-month, 18-month and 24-month visits)
- Food diary log (18-month visit)

	-	0	
-			
•			
-			

*discontinued performing starting in August 2017

Study endpoints

Aim 1:

Primary Endpoint: Change in BMD over 18 months in the GH vs placebo group.

Secondary Endpoints:

- 1. Bone microarchitectural parameters
- 2. Bone strength by FEA

Aim 2:

Primary Endpoint: Change in bone marrow fat in the GH vs placebo group. **Secondary Endpoints:**

- 1. Pref-1.
- 1. Bone formation markers P1NP, ucOC.
- 2. Fasting and 2-hour OGTT insulin.
- 3. Inflammatory markers hsCRP, TNF1 receptor, and IL-6.
- 4. Serum lipoproteins.
- 5. 25-OH vitamin D.

Dual-energy X-ray-absorptiometry (DXA): DXA will be used to measure BMD of the AP and lateral spine (L1-L4), distal radius, total hip, femoral neck and total body. Total fat and fat-free mass measurements will also be obtained.

Quantitative computed tomography (QCT): As DXA may overestimate BMD in obesity,¹⁰⁷ we will perform volumetric QCT of L1 and L2 and of the proximal femur (GE LightSpeed Pro CT scanner, GEHealthcare, Waukesha, WI or Somatom Definition, Siemens Healthcare, Forchheim Germany) and low-dose single slice CT of the abdomen and thigh for body composition.

High-resolution CT: High resolution peripheral QCT will be used to measure volumetric density, morphology and microarchitecture at the distal radius and distal tibia (XtremeCT, Scanco Medical AG[®], Bassersdorf, Switzerland). The outcome variables computed by automated analysis will include volumetric BMD (g hydroxyapatite/cm³) for total, trabecular, and cortical regions; cortical thickness (µm) and porosity measures and trabecular number (mm-1), thickness (mm), and separation (mm). HR-pQCT measurements will be performed at the non-dominant wrist and leg in the absence of a history of fracture.

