Bone Strength: Finite element (FE) models will be generated and analyzed as published⁹³ using software provided by Scanco Medical AG (Bassersdorf, Switzerland) by converting each voxel to an equally-sized brick element,¹¹¹ resulting in FE models with approximately 2 million elements.

MR spectroscopy: Proton MR Spectroscopy of lumbar vertebral and femoral bone marrow (for lipid content), muscle and liver (for lipid content) will be performed with a 3.0 Tesla MR scanner (Siemens Trio, Siemens Medical Systems, Erlangen, Germany) as previously described by our group.^{97, 105, 106, 114-116}

Functional strength testing: Functional strength of the hand and forearm will be determined. Additionally, functional strength of the lower and upper extremities will also be determined.

Endocrine testing:

- fasting GHRH-arginine stimulation test
- GH
- IGF-1
- Bioactive IGF-1
- P1NP and CTX
- Osteocalcin
- Pref-1
- hsCRP and apoB
- IL-6 and TNF-)-α receptors I and II
- Testosterone
- Estradiol and SHBG
- 75-g oral glucose tolerance test (OGTT)

Partners Human Subjects Research Application Form Version Date: June 1, 2005 • Glucose, insulin, hemoglobin A1c, 25(OH) vit D, 1,25 (OH)₂ vitamin D, ionized calcium, phosphorous, iPTH, total cholesterol, LDL, HDL, and triglycerides

For studies involving treatment or diagnosis, provide information about standard of care at Partners (e.g., BWH, MGH) and indicate how the study procedures differ from standard care. Provide information on available alternative treatments, procedures, or methods of diagnosis.

Understanding the pathophysiology of bone loss in obesity may help identify new treatment targets for this important complication. We have excluded potential study subjects with severe bone loss and will refer them for treatment. Mild bone loss, such as we are studying, is not typically treated in young patients, but rather monitored. We will share BMD results with study participants and their physicians (with participants' permission).

Describe how risks to subjects are minimized, for example, by using procedures which are consistent with sound research design and which do not unnecessarily expose subjects to risk or by using procedures already being performed on the subject for diagnostic or treatment purposes.

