Describe explicitly the methods for ensuring the safety of subjects. Provide objective criteria for removing a subject from the study, for example, objective criteria for worsening disease/lack of improvement and/or unacceptable adverse events. The inclusion of objective drop criteria is especially important in studies designed with placebo control groups.

Safety assessments

- 1. IGF-I levels:
 - a. Must have IGF-I within or below the lowest 2 quartiles for age and gender
 - b. Measurements at screening, baseline, 6week, 3 month, 4.5 month, 6 month, 9 month, 12 month, 15 month, 18 month and 24 month
 - c. Dose decrease for IGF-I levels above the upper limit of normal
- 2. Glucose: 2 hour 75 g OGTT: baseline, 6, 12, 18 and 24 months. Fasting glucose at screening, 6 week, 3 month, 4.5 month visits.
- 3. Pregnancy testing: screening, baseline, 6 week, and 3, 4.5, 6, 9, 12, 15, 18 and 24 months (Additional testing will be arranged if lengthened menstrual cycle)
- 4. HbA1c: screening, 6 month, 12 month, 18 month and 24 month

Subjects will be discontinued from the study if they develop

- a. Glucose: fasting \geq 126 mg/dl or 2h GTT \geq 200 mg/dl while they are taking the study medication (between the baseline visit and the day before the 18 month visit)
- b. Diabetes: $HbA1c \ge 6.5\%$
- c. Positive pregnancy test
- d. Severe / intolerable side effects of GH
- e. Development of malignancy
- f. Initiation of the following medications: OCPs

FORESEEABLE RISKS AND DISCOMFORTS

Provide a brief description of any foreseeable risks and discomforts to subjects. Include those related to drugs/devices/procedures being studied and/or administered/performed solely for research purposes. In addition, include psychosocial risks, and risks related to privacy and confidentiality. When applicable, describe risks to a developing fetus or nursing infant.

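### Exploratory analysis 3 uses final GH dose, which is itself adjusted on IGF-1, to ask whether IGF-1 mediates the BMD effect; the exposure should be randomised arm, with IGF-1 as an explicit mediator

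*SAP*

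**What the plan says.** The SAP (Statistical Power and Statistical Analysis, data analysis plan) lists three exploratory questions. The third is "Is the effect of GH on BMD mediated by IGF1", to be answered by "a mediation analysis using a random effects model with final GH dose and a final GH dose time interaction in the treated group". The only terms named are final dose and its interaction with time. No IGF-1 variable or summary is given.

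Earlier in the same plan there is a general mediation method: estimate the treatment effect on the mediator and the mediator effect on the endpoint, multiply the two, and apply the Sobel test. It is introduced with "We will also determine which of the secondary endpoints appears to mediate the treatment effect on an endpoint". The plan also states "For all analyses, an intent-to-treat analysis will be performed".

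Three parts of the Protocol bear on this:
- Specific Aim 1 describes "GH administration for 18 months to increase IGF-1 levels within the normal range".
- Safety assessments, item 1c, reads "Dose decrease for IGF-I levels above the upper limit of normal". Item 1b schedules IGF-1 at 11 time points.
- Endocrine testing lists IGF-1 and, separately, "Bioactive IGF-1". Neither is among the listed study endpoints.

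**The concern.** A mediation analysis needs an exposure whose effect is to be explained, a mediator, and a path from each to the outcome. Here the exposure is final dose among treated patients, which causes two difficulties.

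First, final dose is set after randomisation. An analysis confined to treated patients compares people who ended on different doses, not GH with placebo.

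Second, the dose is cut when IGF-1 is too high. Patients who respond strongly to GH therefore tend to end on lower doses with high IGF-1. This can weaken or reverse the association between final dose and IGF-1, although GH raises IGF-1.

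At stake is the interpretation of the only analysis in the available text that names IGF-1 as a mediator of the BMD effect. A positive dose slope could be reported as support for IGF-1 mediation when it fits a direct GH effect better. A null slope could be read as evidence against mediation when it says almost nothing.

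**Working it through.** The SAP gives no figure for analysis 3. Its general mediation power (80% with 40 subjects, effect 2 units, correlation 0.5) is not disputed. Reading 2 units as 2 SD with equal arms, z = 1/sqrt(1/40 + 1/10) = 2.83 and power is 80.7%.

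**Step 1: what titration does to the dose path.** Let s be a patient's IGF-1 rise per unit dose, D0 the starting dose and H the rise allowed before the upper limit is reached. Suppose dose is cut until the rise equals H. Then final dose = min(D0, H/s) and rise = s × final dose. Assume D0 = 1.0, H = 1.0 and a log-SD of s of 0.3, and take patients one SD either side of the median:
- s = exp(0.3) = 1.35: the uncut rise is 1.35, so dose falls to 1.0/1.35 = 0.74 and the rise is 1.00.
- s = exp(-0.3) = 0.74: the rise is 0.74 and dose stays at 1.00.

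The dose-to-IGF-1 slope between them is (0.74 - 1.00)/(1.00 - 0.74) = -1. If IGF-1 carried the whole BMD effect, the patient on the lower dose would gain more bone.

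**Step 2: effect size from the SAP.** DXA at 0, 1 and 1.5 years gives a time sum of squares of 1.1667. With slope variance 0.000211 and residual variance 0.00092, the SD of a patient's estimated slope is sqrt(0.000211 + 0.00092/1.1667) = 0.0316. The SAP's difference of 0.024 g/cm²/y is then 0.024/0.0316 = 0.76 SD. The 50 completers are taken as 25 per arm (equal allocation assumed).

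**Step 3: simulation.** The assumed inputs, none from the documents, are:
- log-SD of s: 0.2, 0.3 or 0.5
- log-SD of starting dose: 0.2
- H (mean, SD): (1.0, 0), (1.0, 0.2), (0.8, 0) or (1.3, 0.2)
- SD of IGF-1 noise: 0.15

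This makes 3 × 4 = 12 patterns. Entries are the share of trials with a significant positive result (nominal 2.5%), as ranges over the patterns.

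| Model | A: all via IGF-1 | B: direct, proportional to dose | C: direct, equal in all treated |
|---|---|---|---|
| Treated only, dose, no IGF-1 term | 1.4-6.7% | 8.7-22.7% | 2.0-3.2% |
| Both arms, dose 0 in placebo, no IGF-1 term | 61-77% | 77-83% | 67-74% |
| Both arms, randomised arm plus IGF-1 term | 4.1-22.1% | 1.3-7.2% | 2.3-3.7% |

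- Row 1: B exceeded A in all 12 patterns. With no IGF-1-driven dose cut, A and B look alike (9.6-12.4% and 10.3-11.0%). The dose slope is therefore misleading with titration and uninformative without it.
- Row 2 tracks the total GH effect, whatever the pathway.
- Treated only, with an IGF-1 term added: full mediation was detected in 0.0-5.5% of trials in one run and under 2% in another. The dose-to-IGF-1 path was near zero or negative in 8 of 12 patterns.
- Row 3 under confounding: with a direct effect proportional to s and no IGF-1 mediation, mediation was declared in 2.6-20.2% of trials (up to about 21% in a second run). In 3 of 12 patterns this exceeded the rate under true full mediation, for example 15.5% against 8.5%.

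A rerun with the SAP's full random slopes variances and a drop-out rate of 0.36/yr gave the same ordering. Row 1 was then 1.0-6.7% (A) against 9.1-22.3% (B), and row 3 under A was 3.5-23.3%.

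**The case against.** The strongest reply is that the plan already has a mediation method and that analysis 3 only names the exposure terms for it. Much of this stands. The question names IGF-1 as the mediator and the sentence calls itself a mediation analysis. The general method is introduced for secondary endpoints, but the plan also applies it to bone marrow fat, which is the Aim 2 primary endpoint, and to body composition, which is not in the endpoint list. A reader might infer that the plan has no method for IGF-1, or that a missing IGF-1 term is the whole difficulty. The documents do not support either inference. The method plausibly extends to IGF-1, and adding an IGF-1 term does not rescue an analysis confined to treated patients.

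The closing phrase about treated patients could also mean that both arms enter with dose zero in placebo, as the intent-to-treat statement suggests. With an IGF-1 term, that version can address the question: it detected full mediation in 4.2-32.7% of trials, more often than the arm-based model in 10 of 12 patterns. It also declared mediation in up to 13.4% of trials under truth C, and its exposure is still set partly by the mediator.

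Two further objections are fair. The titration inputs are assumed, because the Protocol gives only the direction of the dose change. Part of the SAP was not available for this review and may say more.

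**Conclusion.** The point holds as a minor defect of method. Final dose is post-randomisation and partly caused by IGF-1, so on either treated-only reading the stated model does not estimate how much of the GH effect passes through IGF-1. That follows from the text. The percentages illustrate direction only and rest on the assumed titration.

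A reader might infer that switching to randomised arm makes the mediation result trustworthy. It does not. Randomisation protects the arm-to-IGF-1 path, but IGF-1 change is not randomised, and individual GH sensitivity could drive both IGF-1 and bone. No bound on false mediation can be claimed.

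A reader might also infer damage to the main results. There is none: both primary GH-versus-placebo comparisons are unaffected, and the Aim 1B hypothesis on cortical thickness is not tested by this analysis.

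**What to change.** Replace the last sentence of exploratory analysis 3 with a statement along these lines:

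- Both arms are analysed as randomised, with BMD up to month 18. Arm, not final dose, is the exposure.
- The mediator is change in serum IGF-1, with its summary fixed in advance, for example the mean of on-treatment values from month 6 on, minus baseline. State how patients without such values are handled and count them.
- Mediator model: IGF-1 change on arm and sex.
- Outcome model: the BMD random slopes model with arm-by-time, IGF-1-change-by-time and sex-by-time terms and their main effects.
- The mediated effect is the product of the arm effect on IGF-1 and the IGF-1-change-by-time coefficient, reported with a 95% interval (the delta method already used in the plan, or a bootstrap).
- The result is hypothesis-generating. A final-dose model is not read as evidence for or against IGF-1 mediation.

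If the sponsor intended the two-arm dose model with an IGF-1 term, say so and report it beside the arm-based model.

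The cost is one SAP paragraph and a little programming, with no new measurements. The drawbacks should be stated. Power is roughly 3-23% under full mediation in the assumed models. Confounding of IGF-1 with outcome remains. An average over later visits uses some IGF-1 values taken after the month 12 DXA. Leaving out patients without IGF-1 values would be a post-randomisation exclusion, confined to this analysis.
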